1 STATISTICAL PLAN

1.1 AIM 1

Aim (1). To quantify the relationship between CNS lymphatic measures and beta-amyloid burden.

- Hypothesis (1A). Glymphatic flow and lymphatic collector velocity inversely correlate with beta amyloid measured from 18F-florbetapir PET in older adults with Parkinson's disease.
- Exploratory Hypothesis (1B). In Parkinson's subjects matched for age and sex, glymphatic flow and betaamyloid burden will be worse in patients with versus without mild cognitive impairment (MCI).

A.1.1 Experiment. We will enroll participants with idiopathic Parkinson's disease (n=32; age range=55- 80 years), equally distributed and matched for age and sex between groups with (n=16) and without (n=16) mild cognitive impairment. These populations provide a cohort to evaluate the potential relationship between glymphatic flow and beta-amyloid burden, given the elevated risk of beta-amyloid accumulation associated with both conditions. These patients will form a cohort to be assessed before and after a community-based exercise intervention. Participants will be recruited from Vanderbilt University Medical Center Neurology's Behavioral and Cognitive and Movement Disorder Clinics by Drs. [name] and [name]. Potential participants will undergo a neurological and neuropsychological examination to characterize their medical and neurobehavioral status. Patients will have medical and motor presentation indicated for the community-based exercise program. Those patients with clinically-defined MCI, will be without evidence of vascular cognitive impairment, primary mood disorder, Lewy body disease, or comorbid medical condition that could contribute to cognitive symptoms (e.g. pulmonary, hematologic, metabolic, or vitamin deficiency).

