A.1.3. Statistical concerns. Statistical analyses will be overseen by statistician Co-I [name]. Descriptive statistics, including means, standard deviations, and ranges for continuous parameters, as well as percent and frequency for categorical parameters, will be presented. Tests for normality and homoscedasticity will be made. To test Hypothesis (1A), Pearson or Spearman (depending on normality findings) will be applied to evaluate the relationship between glymphatic flow, measured as the DTIALPS score, and the cortical:cerebellar SUVr, measured from PET. As an exploratory analysis to understand whether the relationship is spatially dependent, correlation testing will be repeated using the regional SUVr measures and corrected p-values reported. Power calculations are based on preliminary data in six MCI subjects in which an inverse correlation (Spearman's alpha =-0.49) was found between SUVr and DTI-ALPS score. With a sample size of 32, we should have 82% power to detect a correlation of -0.49 with two-sided p<0.05. To test Exploratory Hypothesis (1B), we will apply a Student's t-test or Wilcoxon rank-sum test (depending on normality findings), to evaluate whether mean glymphatic flow, measured as the DTI-ALPS score, is different between age- and sex-matched participants with vs. without MCI. Motivation is based on our preliminary data, where we have observed a large effect size (Cohen's d=2.3) in DTI-ALPS score between age- and sex-matched subjects with vs. without MCI.

A.1.4. Impact. Results will for the first time evaluate how the proposed human CNS lymphatic system and levels of beta-amyloid burden are altered in Parkinson's disease. If confirmed, results will motivate the use of evaluating human CNS lymphatic dysfunction with proposed methods for understanding betaamyloid clearance disorders.

A.2. Aims (2). Quantify the glymphatic functioning and beta-amyloid burden response to 12 weeks of a community-based exercise course developed specifically for PD patients.

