procedure will be applied to evaluate differences in SUVr pre vs. post exercise intervention and corrected pvalues will be reported. To gain additional information, a multiple linear regression will be performed using the change in glymphatic flow (DTI-ALPS score) as the dependent variable and degree of compliance and change in beta-amyloid burden as the independent variables. To test Exploratory Hypothesis (2C), we will perform these same comparisons separately for MCI and non-MCI subgroups. Aim 2 hypotheses are exploratory, given limited extant literature defining reliable effect sizes; however, one randomized study (n = 33) demonstrated a 30% divergence in mean plasma levels of a CSF beta-amyloid marker between exercise (-6%) and non-exercise participants (+24%) with MCI. Thus, with the proposed sample size of 32 (each with a measurement before and after intervention), we should have at least 80% power to detect a significant difference in mean DTI-ALPS score pre- vs. post-exercise with at least 80% power and two-sided Type I error=5%. We should also have sufficient power to include two independent variables in the regression model. *A.2.3. Impact.* Results will provide evidence of how CNS lymphatic and beta-amyloid properties adjust in response to regular vigorous exercise in a PD sample.

A.3. Aim (3). Evaluate the degree to which neuroimaging-based response to exercise mediates clinical improvement in neurocognitive functioning and neuropsychiatric symptomatology.

Hypothesis 3.A. Neurocognitive functioning will improve following completion of the exercise intervention. Exploratory Hypothesis (3.B.). Sleep disturbance symptoms will diminish following completion of the exercise intervention.

Exploratory Hypothesis (3.C.). The degree of change glymphatic function and cortical beta-amyloid uptake in response to exercise therapy will be correlated with the degree of improvements in neurocognitive functioning.

Exploratory Hypothesis (3.D.). The degree of change glymphatic function and cortical beta-amyloid uptake in response to exercise therapy will be correlated with the degree of improvements in sleep disturbance symptomatology.

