Patient heterogeneity is a concern. Since other clinical factors can affect brain and cognitive functioning, we plan to control for age and screen for the most common medical conditions that might disproportionally affect outcome assessments. Furthermore, we have selected an age-cutoff that reduces clinical heterogeneity and has extant support for the presence of our conditions-of-interest. Patient recruitment. Vanderbilt University Medical Center's Neurology division has a large clinical volume of adult patients with Parkinson's. Thus, our recruitment target is felt to be reasonable. Patient attrition. We have accounted for a possible 10% attrition/exclusion in our protocol. We will use compliance as a scalar variable, allowing us to retain all patients at follow up, regardless of degree of compliance.

C. Sex as a biological variable. Given the relative infancy of the field of human CNS lymphatic imaging, to our knowledge there is no literature reporting sex differences for all proposed biomarkers of the lymphatic drainage system. Therefore, we have powered our study to specifically address this concern, and subjects will be recruited equally for both sexes and statistical measures are in place to evaluate how each observable varies with biological sex. This should be the first study to report how these properties of the lymphatic system differ with biological sex in humans.

D. Scientific rigor and reproducibility. The need to understand CNS small blood and lymphatic vessels is becoming increasingly recognized, with more than 150 manuscripts published in the last five years on this topic. However, nearly all studies utilize animal models only, and there is much less information available on how this system operates in humans in health or in the presence of clearance disorders such as Alzheimer's disease. One reason for this is that reliable methods for evaluating lymphatics in vivo are underdeveloped. Methods proposed here (e.g., CVR compliance, lymphangiography, glymphatic flow, and CSF flow velocity)

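### The SAP says 10% attrition/exclusion is accounted for, but its enrolled 32 is also the number behind both of its numerical power statements, so 32 contains no such allowance

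*SAP*

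**What the plan says.** The attrition claim is in SAP section B (Limitations and alternative strategies, under patient attrition): "We have accounted for a possible 10% attrition/exclusion in our protocol". The sentence after it says that compliance will be used as a scalar, so that patients are kept at follow-up however much exercise they did.

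The numbers are elsewhere in the SAP:

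- **Enrolment (A.1.1).** "We will enroll participants with idiopathic Parkinson's disease (n=32", split into "groups with (n=16) and without (n=16) mild cognitive impairment".
- **Aim 1 power (A.1.3).** "With a sample size of 32, we should have 82% power to detect a correlation of -0.49 with two-sided p<0.05". The effect size comes from six MCI subjects, in whom "an inverse correlation (Spearman's alpha =-0.49) was found between SUVr and DTI-ALPS score".
- **Aim 2 power (A.2.2).** "with the proposed sample size of 32 (each with a measurement before and after intervention), we should have at least 80% power". No DTI-ALPS change and no SD of change is given.
- **Aim 3 (A.3.2).** Effect sizes from the literature, with no planned sample size or power figure.

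The Protocol (2.1, Overall Design) plans 50 PD patients, 25 with and 25 without MCI. It gives no sample-size rationale and no attrition rate, and it does not connect 50 with the SAP's 32. Protocol 3.1 lists reasons for withdrawing a participant, among them inability to complete the follow-up assessments.

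**The concern.** Accounting for attrition in a sample size means enrolling more patients than the analysis needs. In the SAP the two numbers are the same, and no inflation step, smaller evaluable number or replacement rule appears. Keeping non-compliers who return for follow-up does not fill the gap left by patients who withdraw, are excluded, or lack a usable scan.

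A reader of section B would believe that the stated power already survives a 10% loss. On the SAP's own numbers it does not. The analyses most exposed are the pre-post comparisons of Aim 2. The SAP labels them exploratory, but they address the Protocol's primary objective and need two complete imaging sessions per patient.

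**Working it through.** **Inputs.** Enrolment 32 (SAP A.1.1); r = -0.49, two-sided 5%, 82% power at 32 (SAP A.1.3); 32 pre/post pairs with at least 80% power (SAP A.2.2); 10% loss (SAP section B); enrolment 50 (Protocol 2.1).

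**1. Reproduce the SAP's 82%.** Fisher z: power = Φ(atanh(0.49) × √(n − 3) − 1.96), with atanh(0.49) = 0.536.

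At n = 32: 0.536 × √29 = 2.887; 2.887 − 1.96 = 0.927; Φ(0.927) = 82.3%. The stated figure is reproduced with all 32 patients analysed.

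**2. Is there a 10% margin in 32?** 32 × 0.9 = 28.8, so 28 to 29 patients remain. To keep 32 evaluable, enrolment must be 32 / 0.9 = 35.6, rounded up to 36.

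**3. Power for r = -0.49 at other numbers (same formula).**

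| Analysed n | Power |
|---|---|
| 32 | 82.3% |
| 31 | 81.0% |
| 30 | 79.5% |
| 29 | 78.0% |
| 28 | 76.4% |
| 45 | 93.5% |

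By this formula 32 can lose one patient and stay above 80%; a 10% loss is about three. Simulating the Pearson test gives slightly higher values, with the same conclusion at 28 to 29: 83.4% at 32, 79.6% at 29 and 78.0% at 28.

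**4. Which losses reach which analysis.** Hypothesis 1A correlates DTI-ALPS with SUVr, and Aim 1 describes no follow-up scan. A patient who leaves during the 12 weeks already has baseline MRI and PET. The 28 and 29 rows therefore apply to 1A only if the entire 10% consists of baseline exclusions or unusable baseline MRI/PET. The Aim 2 paired tests are exposed to both baseline and follow-up losses, so 28 to 29 pairs is the right count for them after a full 10% loss.

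**5. Aim 2 power.** This cannot be recomputed, because A.2.2 gives no effect size or SD. For illustration only, assume an effect with exactly 80% power at 32 pairs. By the noncentral t distribution for a two-sided paired t-test this is d = 0.511. The same d has 75.7% power at 29 pairs and 74.2% at 28.

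**6. If 50 is the enrolment.** 50 × 0.9 = 45 remain, which is more than 32. Power for r = -0.49 at 45 is 93.5%.

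**The case against.** The strongest reply is that the attrition sentence refers to the protocol, and the Protocol enrols 50. Even after a 10% loss 45 remain, well above the 32 on which power is stated. This stands in part: if 50 is operative there is no power shortfall, and a reader who infers that the trial as a whole has no room for attrition goes further than the documents allow. But the Protocol does not present 50 as an attrition margin, a 10% allowance on 32 gives 36 rather than 50, and the SAP itself enrols 32. The reply moves the problem to an unreconciled sample size; it does not show that the SAP's statement is supported.

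A second reply is that 1A is a baseline analysis. This stands. A reader might infer that ordinary dropout takes 1A below 80%, but most of the withdrawal reasons in Protocol 3.1 act after baseline. The SAP's radiology review (A.1.2.2) could lead to baseline exclusions, but no rate is given. The 10% is also described as possible, not expected.

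Third, the shortfall is small. That is fair: one loss still leaves 81.0%, so it would be too strong to say that the stated power survives only with no loss at all. Nor is every aim affected in the same checkable way, since Aim 3 states no power figure.

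**Conclusion.** The claim that 10% attrition/exclusion is accounted for is not supported by the SAP's own numbers: enrolled 32 equals the 32 in both numerical power statements.

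The size depends on which enrolment is operative.

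- **If 32:** a full 10% loss leaves 28 to 29 pairs for Aim 2. The corresponding power is unknown; 74-76% is an illustration resting on an assumed effect. For 1A, about 76-78% is a worst case, assuming Fisher z, a true correlation of -0.49, and the whole loss occurring at baseline.
- **If 50:** 45 remain and nothing is short, but 32 and 82% are then not the figures for the design.

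The documents do not support concluding that the trial is underpowered, or that 1A will fall below 80% because of dropout during the exercise period. What they show is a stated safeguard that is absent from the calculation, with a modest effect on power at most.

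**What to change.** 1. Reconcile the SAP's 32 with the Protocol's 50 and state which is the planned enrolment. The remaining steps depend on this.
2. Give enrolled and evaluable numbers separately for the baseline analysis (Hypothesis 1A) and for the pre-post analyses (Aims 2 and 3), since different losses apply to each.
3. Restate power at the evaluable number. If 50 is the enrolment, replace 32 and 82% with the figures for that design; after a full 10% loss these are 45 and about 93.5% for 1A.
4. If 32 is the enrolment, delete the attrition claim, give 28 to 29 pairs for Aim 2, and report 76-78% as the worst case for 1A.

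Replacing patients lost before baseline imaging would not be enough. It raises enrolment above 32 and leaves pre-post losses uncovered.

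The cost is wording in the SAP and agreement on one sample size across the two documents. If 32 is operative, the stated power becomes slightly less favourable.
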